## **STUDY OBJECTIVES AND OUTCOMES**

### **OBJECTIVES**

#### **Primary Objective:**

- To explore BNA changes from baseline to endpoint on 1) efficacy of core MDD symptoms and, 2) improvement of cognitive dysfunction with acute treatment of flexible dose vortioxetine in adult outpatients with MDD and subjective complaints of cognitive dysfunction.

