## **OUTCOMES**

### **Primary Outcome:**

The primary outcome of this study is to explore changes in BNA patterns from baseline to endpoint with 1) antidepressant response status; response defined as  $\geq 50\%$  change in total MADRS score from baseline to endpoint and, 2) change in cognitive function defined as change from baseline to endpoint on change in total number of correct symbols on the DSST .

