## **STATISTICAL ANALYSES**

### **Primary Efficacy Analysis**

The primary endpoint is the change from Baseline in the MADRS and DSST score. The primary endpoint will be analyzed using analysis of covariance (ANCOVA), with treatment and center as fixed factors, and baseline score as covariate. The p-values, least squares (LS) treatment means, difference between the LS treatment means, and 95% CIs for the treatment differences will be displayed.

This is a pilot study that is intended to evaluate the extent of to which BNA technology can provide clinically valuable information, and to provide data that will help design a future confirmatory study. Because this is an exploratory study, no formal sample size calculation was performed; rather, sample size has been based on that which is generally accepted by the medical community for a study of this nature. In order to strengthen the level of confidence of the results, the BNA test is performed twice before the subject is given medication to provide repeatability and two additional times during the course of treatment to allow the identification of any potential trend that may occur as a result of treatment.

The relationship between changes in BNA and BNA total mean change from baseline and endpoint will be analyzed. Changes in BNA from baseline will also be analyzed by groups defined on endpoint status (e.g. response to MADRS, remission, change in DSST).

Statistical analysis should also consider the fact that changes in brain networks may be independent of symptoms or neurocognitive scores; thus, the analysis of BNA changes across treatment duration should be also performed independently. In other words, it is possible that BNA conveys information that is not found in other methods; trying to find correlations may limit the correct interpretation. Therefore, robust trends found in BNA scores should be further researched, regardless of finding correlations to symptoms or neurocognitive tests. For example, it could be that a change in BNA, without a significant change in symptoms, means that if the treatment will be continued for a few more weeks, a delayed improvement will be found; etc.

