In addition, BNA change analysis will be performed. Each subject participating in the drug treatment arm of the study is assigned similarity indices that quantify the degree to which his/her individual BNA repertoire match that of each group BNA. The score is computed twice for each subject – once for pre-treatment, and once for post-treatment, the difference between them being termed 'BNA change'.

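### The analysis labelled primary contains no BNA term although BNA change is the primary outcome, one BNA sentence has no clinical variable, and BNA change against continuous DSST change has no stated analysis

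*Combined protocol and SAP*

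**What the plan says.** The Primary Objective puts the biomarker first: "To explore BNA changes from baseline to endpoint on 1) efficacy of core MDD symptoms", with improvement of cognitive dysfunction as its second limb. The Primary Outcome section agrees: "The primary outcome of this study is to explore changes in BNA patterns from baseline to endpoint with 1) antidepressant response status", and, as its second part, "change in cognitive function defined as change from baseline to endpoint on change in total number of correct symbols on the DSST". The Secondary Objectives list efficacy on depression scales and change in cognitive function.

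The Primary Efficacy Analysis section reads differently: "The primary endpoint is the change from Baseline in the MADRS and DSST score". That endpoint is to be "analyzed using analysis of covariance (ANCOVA), with treatment and center as fixed factors, and baseline score as covariate". BNA enters two paragraphs later, in two sentences. The first is "The relationship between changes in BNA and BNA total mean change from baseline and endpoint will be analyzed". The second is "Changes in BNA from baseline will also be analyzed by groups defined on endpoint status (e.g. response to MADRS, remission, change in DSST". Neither is called primary.

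**The concern.** The objectives and the analysis section disagree about what is primary. If the analysis section is followed, the result reported as primary concerns symptom and cognition scores under open-label vortioxetine. The question for which the pilot was set up, whether BNA tracks clinical change, is left to two loosely worded sentences.

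The first of those sentences has a further problem. If the BNA total is built from the scores being correlated with it, the relationship is positive by construction and says nothing about patients. The pilot is meant to inform a confirmatory study, so an association of that kind, or an unplanned choice of BNA score and DSST grouping, could carry over into the next design.

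**Working it through.** The plan states no sample-size or power figure to reproduce. The check is mainly a comparison of sections, followed by two illustrations.

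**1. Section against section**

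| Section | Status given | BNA involved? | Clinical variable |
|---|---|---|---|
| Primary Objective | primary | yes | core symptoms; cognition |
| Primary Outcome | primary | yes | MADRS response (binary); DSST change (continuous) |
| Secondary Objectives | secondary | not in the efficacy and cognition items | depression scales; cognition |
| Primary Efficacy Analysis, ANCOVA | primary | no | MADRS change; DSST change |
| Same section, first BNA sentence | none given | on both sides | none |
| Same section, second BNA sentence | none given | yes | groups by MADRS response, remission, DSST change |

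The Secondary Efficacy Analyses section lists MADRS change again, so that variable is both primary and secondary within the statistical section.

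**2. Is BNA change against continuous DSST change planned elsewhere?**

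- Secondary Outcomes item 2 relates BNA change to many scales, but its cognition list omits the DSST.
- Item 4 compares BNA change across groups with and without DSST improvement and gives no cut-off.
- Item 5d gives a 70% DSST cut-off, but for prediction from pre-treatment BNA.
- The path analysis uses continuous DSST and MADRS change and has no BNA variable.
- BNA Analysis defines BNA change as a pre/post difference ("The score is computed twice for each subject") without linking it to MADRS or DSST. Its search for predictors of response names no model.
- One secondary objective sets BNA change beside clinical change in symptoms and cognition, but no analysis is attached to it.

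So grouped comparisons are planned, and an association on the continuous DSST scale is not.

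**3. Illustration: the first BNA sentence taken literally**

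Assume that the BNA total is the mean of k independent component changes with equal variance s². Then

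- cov(component, total) = s²/k and var(total) = s²/k;
- r = (s²/k) / sqrt(s² × s²/k) = 1/sqrt(k).

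At n = 40 the two-sided 5% critical value is |r| of about 0.312.

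| k | 1/sqrt(k) | Simulated null data sets with p < 0.05 |
|---|---|---|
| 3 | 0.58 | 98–99% |
| 4 | 0.50 | 92–93% |
| 8 | 0.35 | 62% |

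For k = 4, t = 0.50 × sqrt(38/0.75) = 3.56 on 38 degrees of freedom, p = 0.001. The value of k, the independence and the equal variances are all assumptions.

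**4. Illustration: what the intended analyses could show (two-sided 5%, 80% power)**

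- BNA change against DSST change: detectable |r| = tanh((1.960 + 0.842)/sqrt(n − 3)). At n = 40 this is tanh(2.802/6.083) = 0.43. With an assumed 36, 32 or 28 evaluable subjects it is 0.45, 0.48 or 0.51. The plan gives no dropout rate.
- BNA change in responders against non-responders at n = 40: detectable standardised difference = 2.802 × sqrt(1/n1 + 1/n2). A 20/20 split gives 0.89 and a 12/28 split gives 0.97. Assumed response rates of 30% to 60% stay within that range.

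**The case against.** **The second BNA sentence.** A reader might infer that the only BNA association in the plan is BNA with itself, or that the DSST half of the primary outcome is never analysed. The documents support neither. The second sentence ties BNA change to MADRS response, remission and DSST change, and Secondary Outcomes item 4 adds a comparison across DSST-improvement groups. This part of the objection stands. What remains is narrower: the sentence names no BNA score, task, model or test, and it turns a continuous outcome into groups without a rule.

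**A drafting slip.** One BNA in the first sentence may stand for a clinical total score. In that case no part-whole correlation would be run and the percentages above would not apply. The documents do not settle this. Either way the sentence needs correcting, and the figures are only illustrative.

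**No headline and no success rule.** A reader might also infer that the trial would declare success on a spurious BNA correlation. The sentence is not labelled primary, the study is described as an exploratory pilot, and no success criterion is set. The ANCOVA also asks for differences between treatment means although all enrolled subjects are to receive vortioxetine, so a formal treatment win on MADRS or DSST is not estimable as written. This stands against any claim of false success, but it does not supply a primary analysis that includes BNA.

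**Deliberate independence from symptoms.** The section closes by warning that looking for correlations could mislead and that BNA trends deserve study in their own right. That justifies an additional BNA-only analysis. It does not explain why the primary outcome, which is defined by association with clinical change, lacks a matching primary analysis.

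**Conclusion.** The point holds in this form. The analysis labelled primary omits BNA and so cannot address the primary objective. One of the two BNA sentences contains no clinical variable. The other covers MADRS response in outline but leaves the continuous DSST change without a stated association analysis. These conclusions rest on the text alone.

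The part-whole figures (about 60% to 99% of null data sets significant for k = 8 down to 3, n = 40) depend on an assumed structure for an undefined total. They show what a literal reading could produce, not what the trial will produce. The mismatch should be corrected before analysis, because the primary question currently has no specified primary analysis.

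**What to change.** In the Primary Efficacy Analysis section:

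1. Name as primary the association of BNA change, baseline to Week 8, with (a) MADRS response, taken as the decrease of at least 50% in Outcome Definitions, by comparing BNA change between responders and non-responders; and (b) change in DSST correct symbols on its continuous scale. Give the model for each, with estimates and 95% intervals.
2. Name one BNA score from one task as the primary measure. The protocol describes several scores and several tasks, and one task may be dropped if recording time reaches 60 minutes.
3. State which measurement is the pre-treatment value. Appendix I schedules BNA at screening and baseline, but the DSST before treatment only at screening.
4. Relabel the MADRS and DSST change analyses as secondary, in line with the Secondary Objectives.
5. Replace the BNA-to-BNA sentence with the relationship between BNA change and the two clinical outcomes in step 1. Do not correlate a BNA score with a total that contains it.
6. Keep the by-group comparisons and the symptom-independent BNA analysis as exploratory, and give a rule for any DSST grouping.

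This changes wording only and needs no new data, since BNA and the DSST are both scheduled before treatment and at Visit 10. The cost is that MADRS and DSST improvement can no longer be presented as the primary result. With 40 subjects the primary associations will also be imprecise: the 95% limits around a zero correlation are about ±0.31.

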### **Secondary Efficacy Analyses**

Change from Baseline in TMT A, TMT B, , PDQ, MGH-CPFQ, UPSA, percentage of productivity loss (WLQ), MADRS, CGI-S, and CGI-I will be analyzed at all time points (where rated) using ANCOVA model similar to the one described above for the primary endpoints.

MADRS responders (defined as a >50% decrease from Baseline), MADRS remission (defined as a MADRS total score <10). CGI-S remission (CGT-S2), and CGI-I response (CGI-I2) will be analyzed at all time points by logistic regression, adjusting for baseline score and treatment.

Proportion of cognitive dysfunction improvement that is not due to an improvement in depressive symptoms will be analyzed using a path analysis with change from Baseline in DSST score and change from Baseline in MADRS total score as endogenous variables.

C-SSRS will be summarized at all time points using descriptive techniques.

All statistical tests will be 2-sided and at the 5% level of significance. Ninety-five percent confidence limits will be presented together with the p-values.

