### Number of Subjects:

40 subjects enrolled. For purposes of IRB reporting, an enrolled subject is one who signs informed consent. For purposes of data analysis and reporting to the funding organization, an enrolled subject is one who meets all inclusion criteria and no exclusion criteria and completes the baseline visit including the baseline BNA.

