**Antidepressant medication (vortioxetine)**

At the time of informed consent, the subject will be instructed about the risks and benefits of the vortioxetine that will be used throughout the study.

The potential risks of the medication will be based upon the FDA-approved package insert labeling for vortioxetine and will include, but not limited to, spontaneous reported adverse events and potential serious adverse events. Source documents will contain documentation that the subject was informed of risks of treatment and that there was adequate time to read and discuss this information with the clinician during the informed consent process.

The FDA-approved package insert for vortioxetine recommends a starting dose of 10 mg/day, increased to 20 mg/day as tolerated. The maximum dose is 20 mg/day, and the minimum dose is 5 mg/day if a higher dose is not tolerated. This allows for individualized “flexible” dosing for efficacy and tolerability.

In order to standardize this flexible dosing, all subjects will be started at 10 mg/day following visit 2 (baseline). The dose will be increased to a maximum of 20 mg/day after visit 4 (2 weeks of treatment) if tolerated by the subject. Dose decreases may occur at any time until Visit 8 for tolerability issues, to a minimum dose of 5 mg/day, and the dose may be re-increased if the tolerability issue resolves.

No dose adjustments may take place after visit 8 through the end of treatment (Visit 10).

Safety, tolerability, and depressive symptoms/function assessments will occur at baseline and each subsequent visit through the end of the study. While this is an exploratory analysis, the impact of treatment at various points in the study will be analyzed. Baseline assessments will occur prior to the subject receiving medication.

Drug accountability will be recorded at all visits. Subjects failing to meet at least 80% adherence to study medication between study visits will be discontinued from the study.

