**Other Risks**

Whenever a subject is determined to be at risk for suicide during a clinical visit by the examining clinician, she or he will be escorted to the nearest emergency room.

We will not share information about subjects' participation in this study with others to minimize risks relative to subjects' privacy. Every effort will be made to keep participation confidential. These issues will be clearly stated in consent forms and discussed with participants during the informed consent procedure.

Consistent with good clinical practice, safety will be monitored by each subject's assigned clinician at each study visit. This clinician will be available 24 hours a day by page. The PI will supervise all study activities including ratings, reported adverse events, laboratory tests, and vital signs. Subjects will be monitored for adverse events at each visit and during phone communications with the clinician. All adverse events will be recorded.

All procedures will aim to minimize subject discomfort, and no subject will be asked to engage in research procedures not outlined in the consent form. All adverse events will be reported to the PHRC according to PHRC guidelines.

Subjects who are judged to experience a worsening of depressive symptoms as manifested by a CGI-Improvement rating of 6 or more (1=Very much improved, 2=Much improved, 3=Minimally improved, 4=No change, 5=Minimally worse, 6=Much worse, 7=Very much worse) or per the investigator's opinion for 2 consecutive visits the subject may be removed from the study and provided referrals as appropriate.

Subjects with MDD will be offered three months of follow-up care at the completion of the study (or if they are required to discontinue for any reason) in which they will be seen by study staff for routine outpatient management of their MDD. Subjects will receive referrals to clinicians in their communities, either at the end of the 3 month period, or sooner upon their request or circumstances require such a referral as determined by the investigator.

If a subject becomes pregnant or is found to be abusing substances during the study, he or she will be discontinued from the study and given referrals.

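### The weekly scales are analysed one visit at a time, and the plan does not say how early leavers or early-termination scores enter the Week 8 result

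*Combined protocol and SAP*

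**What the plan says.** **Model.** Primary Efficacy Analysis names change from baseline in MADRS and DSST as the primary endpoint: "The primary endpoint will be analyzed using analysis of covariance (ANCOVA), with treatment and center as fixed factors, and baseline score as covariate". Secondary Efficacy Analyses carries this model to the other scales, which "will be analyzed at all time points (where rated) using ANCOVA model similar to the one described above for the primary endpoints". Response and remission "will be analyzed at all time points by logistic regression, adjusting for baseline score and treatment". No visit term, subject term or within-subject covariance appears anywhere.

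**Rating schedule.** Appendix I has MADRS, CGI-S, PDQ, MGH-CPFQ and WLQ at screening, baseline and all eight later visits. CGI-I starts at Visit 3. DSST, TMT and UPSA are rated only at screening and in the last column, which serves either Visit 10 or early termination.

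**Leaving the study.** Under Other Risks, a CGI-I of 6 or more, or the investigator's opinion, is the trigger: "for 2 consecutive visits the subject may be removed from the study and provided referrals as appropriate". Under Antidepressant medication (vortioxetine): "Subjects failing to meet at least 80% adherence to study medication between study visits will be discontinued from the study". Data and Safety Monitoring also lets the principal investigator end participation in the subject's best interest.

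**Missing data.** No method, analysis set for leavers or definition of endpoint for leavers is given. The reference list holds a paper comparing MMRM with LOCF (entry 56), but the analysis sections do not cite it.

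**The concern.** If leaving depends on scores already recorded, the subjects still rated at Week 8 are a selected group, and an ANCOVA on them alone describes that group. A leaver's ratings enter the ANCOVAs of the earlier visits but contribute nothing to Week 8, although up to seven of them exist and predict what the Week 8 score would have been. Using the ET rating as the final value has a different fault: it is carry-forward, and it freezes subjects before the full treatment period has passed.

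The plan allows either reading, so the choice could be made after the data are seen. MADRS change is a named primary endpoint, and the study is meant to inform the design of a confirmatory trial. The by-visit response and remission regressions have the same gap.

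**Working it through.** **1. Inputs.** From the documents: "40 subjects enrolled", weekly ratings to Week 8, and possible removal after two consecutive visits of marked worsening. The plan has no figure to reproduce, since "no formal sample size calculation was performed" and no SD or dropout rate is stated. Everything else below is an assumption.

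**2. Identity.** With a share d of leavers,

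completer mean − all-subject mean = d × (completer mean − leaver mean).

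If leavers improve less by 5, 10 or 15 MADRS points, the overstatement is:
- d = 0.10 (4 of 40): 0.5, 1.0, 1.5
- d = 0.20 (8 of 40): 1.0, 2.0, 3.0
- d = 0.30 (12 of 40): 1.5, 3.0, 4.5

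**3. Simulation.** Single arm, N = 40, 300 runs per scenario.
- Baseline: mean 32, SD 4.
- Individual Week 8 change: mean −15, SD 8, 10 or 12, reached along the curve (1 − e^(−w/3)) / (1 − e^(−8/3)).
- Visit noise: SD 3.5. Scores are held within 0 to 60.
- Removal: probability 0.5 or 1.0 once two consecutive ratings are at least 3 points above baseline (a stand-in for the CGI-I trigger).
- Other dropout, unrelated to scores: 0 or 2% per week.

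The Week 8 change was estimated by ANCOVA on observed cases, by the final value including the ET rating, and by a multivariate-normal likelihood fit to all visits with unstructured covariance. Full data means the same subjects with nobody lost.

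| SD | Removal prob. | Other/week | Dropout | Full data | Observed-case ANCOVA | ET as final | Likelihood fit |
|---|---|---|---|---|---|---|---|
| 8 | 0.5 | 0 | 3.0% | −14.94 | −15.45 | −14.85 | −14.97 |
| 8 | 0.5 | 2% | 13.8% | −14.67 | −15.16 | −14.24 | −14.65 |
| 8 | 1.0 | 0 | 4.2% | −14.73 | −15.42 | −14.57 | −14.75 |
| 8 | 1.0 | 2% | 15.0% | −14.85 | −15.51 | −14.32 | −14.87 |
| 10 | 0.5 | 0 | 5.2% | −14.48 | −15.50 | −14.40 | −14.52 |
| 10 | 0.5 | 2% | 16.4% | −14.60 | −15.67 | −14.19 | −14.67 |
| 10 | 1.0 | 0 | 7.0% | −14.67 | −15.98 | −14.49 | −14.71 |
| 10 | 1.0 | 2% | 17.5% | −14.83 | −16.15 | −14.33 | −14.89 |
| 12 | 0.5 | 0 | 7.7% | −14.62 | −16.35 | −14.57 | −14.71 |
| 12 | 0.5 | 2% | 18.1% | −14.34 | −16.12 | −13.99 | −14.43 |
| 12 | 1.0 | 0 | 9.9% | −14.37 | −16.57 | −14.30 | −14.54 |
| 12 | 1.0 | 2% | 20.9% | −14.37 | −16.61 | −13.99 | −14.62 |

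**4. Reading the table.**
- Observed cases overstate improvement in all 12 rows, from 15.16 − 14.67 = 0.49 to 16.61 − 14.37 = 2.24 points.
- ET as final understates it in all 12 rows, from 14.62 − 14.57 = 0.05 to 14.85 − 14.32 = 0.53.
- The likelihood fit is at worst 14.62 − 14.37 = 0.25 away.
- The gap between the two readings of the plan runs from 15.45 − 14.85 = 0.60 to 16.61 − 13.99 = 2.62.
- Adding 2% per week of unrelated dropout hardly moves the overstatement (SD 10, removal 1.0: 1.31 without, 1.32 with). The overstatement comes from removal tied to scores.

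**5. Scale.** Ignoring the 0 to 60 limits and baseline adjustment, the SD of the observed change is √(SD² + 2 × 3.5²), which is 9.41, 11.16 or 12.98. Dividing by √40 gives an SE of 1.49, 1.76 or 2.05. The overstatement is therefore about 0.3 SE (0.49 / 1.49) to 1.1 SE (2.24 / 2.05).

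**The case against.** A reader might infer that the plan drops leavers, that its rules remove worsening subjects, and that Week 8 improvement is therefore overstated. The documents do not support that.
- The phrase about where scales are rated most naturally points to the rating schedule, since some scales are weekly and others are not. It is not an observed-case rule.
- The last column of Appendix I could supply a final score for every leaver attending an ET visit, and on that reading the bias is small and runs the other way.
- Removal for worsening is permissive and needs two consecutive visits.
- The adherence rule is mandatory but does not depend on outcome.

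All of this stands, and it makes the direction conditional.

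It can also be said that the study is an exploratory pilot centred on BNA, that the possible bias is mostly below one SE, and that a repeated-measures model is not a full cure. Those points stand too. Removal on investigator opinion may rest on information no scale records, and removal triggered by CGI-I is not captured when PDQ or WLQ is modelled alone. The simulation tied removal to the scale being modelled, which favours the likelihood fit.

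What the objection does not remove is the open choice between two readings, or the fact that neither uses a leaver's earlier ratings to estimate Week 8. The ET column also gives no value for the weeks between leaving and Visit 10, although analyses are planned at every rated time point.

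**Conclusion.** The point holds in conditional form. The plan analyses weekly scales by separate ANCOVAs and leaves the handling of leavers and ET scores unstated. If only observed cases are used, Week 8 MADRS improvement would probably be overstated, by about 0.5 to 2.2 points in the scenarios tried. If ET scores fill the Visit 10 slot, it would tend to be understated by about 0.05 to 0.5.

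These sizes rest entirely on the assumed SDs, trajectory, removal probability and dropout of 3% to 21%. The documents establish neither a direction nor a size. The change is worth making before analysis because the data needed are already collected. It does not threaten the study.

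**What to change.** - **Weekly scales with a baseline rating** (MADRS, CGI-S, PDQ, MGH-CPFQ, WLQ): one repeated-measures likelihood model per scale, with visit, centre, baseline and baseline-by-visit. Use it for the primary MADRS change as well, so that there is one MADRS estimate. All subjects receive vortioxetine, so no treatment term is needed.
- **Covariance:** unstructured, with a pre-stated simpler fallback such as Toeplitz. Eight visits give 8 × 9 / 2 = 36 parameters for 40 subjects. For WLQ, given only to employed subjects, start with the simpler structure.
- **CGI-I:** it has no baseline rating, so adjust for baseline CGI-S, for example.
- **ET ratings:** assign them to the week in which they were taken. Take the Week 8 mean change as the main estimate.
- **Sensitivity:** keep per-visit ANCOVA, stating which subjects and values it uses.
- **DSST, TMT, UPSA:** keep ANCOVA, define endpoint, and say whether an ET score counts.
- **Response and remission:** state how leavers are counted. Report leavers by week and reason.

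The cost is analysis-plan wording and slightly more programming, with no extra subjects, visits or ratings. The price in assumptions is missing-at-random, which is not assured for removals based on investigator opinion, or on CGI-I when another scale is modelled. The report should say so.

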**Main Criteria for Inclusion:**

- The subject has single episode or recurrent MDD (acute onset of recurrence of recurrent MDD with poor inter-episode recovery) (inter-episode periods cannot meet full MDD criteria) as the primary diagnosis according to DSM-IV-TR criteria. The current MDE will be confirmed using the Mini International Neuropsychiatric Interview (MINI V6.0.0).
- The subject has a MADRS total score  $\geq 26$ .
- Subject reports subjective cognitive dysfunction (such as difficulty concentrating, slow thinking, and difficulty in learning new things or remembering things).
- The reported duration of the current MDE is at least 3 months and no longer than 24 months.
- The subject is a man or woman between 18 and 65 years old, inclusive.
- Right-handed, normal (corrected) vision, and normal hearing.

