### **Visits 2-10**

#### All Subjects

- Subjects who meet all inclusion criteria and no exclusion criteria following the screening visit will enter the study. Weekly study visits will be conducted for efficacy, safety, and tolerability. No dose changes will be allowed after Visit 8.
- A baseline EEG/BNA will be taken before the subject begins taking vortioxetine and follow-up EEG/BNA readings will be taken at Visit 4, and Visit 10 (or last study visit if a subject is withdrawn early).
- Vital signs, review of adverse events, study drug accountability and clinician- and patient-rated scales will be conducted at specific study visits.

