**APPENDIX I - SCHEDULE OF EVENTS**

Visit #	Screen 1	Baseline 2	3	4	5	6	7	8	9	10 (or ET)
Day	-2 to -14	0	7	14	21	28	35	42	49	56
Week	-1 to-2	0	1	2	3	4	5	6	7	8
Informed Consent	X									
Incl/Excl Criteria	X	X								
MINI	X									
ASRS	X									
Medical and Psychiatric History	X									
Demographics	X									
Physical Exam	X									
Laboratory tests, urinalysis, urine pregnancy test and urine drug screen 	X									
Vital signs and weight 	X	X	X	X	X	X	X	X	X	X
Height		X								
12-Lead ECG	X									
HDRS (28-item)	X	X	X	X	X	X	X	X	X	X
QIDS-SR-16	X	X	X	X	X	X	X	X	X	X
MADRS	X	X	X	X	X	X	X	X	X	X
DSST	X									X
UPSA	X									X
TMT-A AND TMT-B	X									X
Stroop Test	X									X
MGH-CPFQ	X	X	X	X	X	X	X	X	X	X
PDQ	X	X	X	X	X	X	X	X	X	X
CGI-S	X	X	X	X	X	X	X	X	X	X
CGI-I			X	X	X	X	X	X	X	X
WLQ	X	X	X	X	X	X	X	X	X	X
C-SSRS 	X	X	X	X	X	X	X	X	X	X
Concomitant therapy	X	X	X	X	X	X	X	X	X	X
Study drug dispensed		X	X	X	X	X	X	X	X	
Study drug accountability			X	X	X	X	X	X	X	X
Adverse events	X	X	X	X	X	X	X	X	X	X
EEG (BNA reading)	X	X		X						X

may be repeated at investigator's discretion

including body temperature (oral), blood pressure and pulse.

C-SSRS lifetime version at screen only; Since Last Visit version at V2-10

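### Visit-by-visit logistic regression in one arm of 40 gives no treatment odds ratio at any week and, if early events are rare, may have no estimate at all; report weekly proportions with exact intervals.

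*Combined protocol and SAP*

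**What the plan says.** - **Model.** Secondary Efficacy Analyses names four binary outcomes: MADRS response, MADRS remission, CGI-S remission and CGI-I response. They "will be analyzed at all time points by logistic regression, adjusting for baseline score and treatment". The section adds two-sided 5% tests, with 95% limits shown beside the p-values.
- **Visits.** Visits 2-10 state that "Weekly study visits will be conducted for efficacy, safety, and tolerability". The Schedule of Events rates MADRS and CGI-S at every visit from screening to Visit 10, and CGI-I from Visit 3 on. That makes eight post-baseline time points, Weeks 1-8.
- **Size.** The synopsis gives "40 subjects enrolled". For data analysis, "an enrolled subject is one who meets all inclusion criteria and no exclusion criteria and completes the baseline visit including the baseline BNA". Primary Efficacy Analysis states that "no formal sample size calculation was performed".
- **Entry severity.** "The subject has a MADRS total score" of at least 26.
- **Cut-offs.** Response in the model section is "MADRS responders (defined as a >50% decrease from Baseline". MADRS remission is printed there as below 10, under Outcome Definitions as 10 or less, and under Secondary Outcomes as below 11.
- **Arms.** The safety outcome describes eight weeks of open-label treatment in all subjects, and the dosing text starts everyone on the same dose after Visit 2.

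The plan has no minimum event count, no exact or penalised method, and no descriptive fallback for these outcomes. C-SSRS, by contrast, is explicitly descriptive.

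**The concern.** A logistic model adjusted for treatment is a two-arm comparison, and this study has one arm. With the constant term removed, the model answers only whether baseline severity predicts the outcome. None of the stated objectives asks for that as such.

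The model also needs enough events to be fitted. From an entry score of 26 or more, remission is a large fall to reach by Day 7, and the sample is small. If no one has the event, or if those with and without it do not overlap on baseline score, the maximum-likelihood estimate does not exist. Software then reports non-convergence or an extreme odds ratio, and the plan asks for a p-value and limits beside it.

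At stake is what the pilot passes on. Its declared use is to help design a confirmatory study. That needs the weekly proportion in response or remission with its uncertainty, which this model does not report. With no fallback set in advance, the analyst would choose a rescue method after seeing the counts.

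**Working it through.** The plan gives no power, event rate or dropout figure with its 40 subjects, so there is no figure of its own to reproduce.

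**1. Treatment term.** The columns are intercept (all 1), baseline score, and treatment (all 1). The matrix has rank 2 for 3 columns, so the treatment coefficient cannot be estimated at any visit, whatever the number of events. For CGI-I the baseline adjustment is undefined too, because the scale is first rated at Visit 3.

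**2. Fall needed from a MADRS of 26.**
- Remission below 10: 26 - 9 = 17 points (65%).
- Remission at 10 or less (or below 11): 26 - 10 = 16 points (62%).
- Response above 50%: more than 13 points.

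Higher baselines need larger falls. Remission is therefore harder to reach than response.

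**3. Event counts.** Early rates are not documented, so a range is assumed. With N = 40 and rate p, P(no events) = (1 - p)^40, for example 0.95^40 = 0.129. P(fewer than 5) is the binomial probability of 0 to 4 events.

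**4. Existence of the estimate, baseline-only model.** Simulation used 20,000 trials per rate. Baseline MADRS was Normal(31, SD 4), rounded and limited to 26-50 (assumed), with events independent of baseline. A trial counted as having no estimate if there were no events or if the two groups' baselines did not overlap.

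| Assumed rate | Expected events | P(no events) | P(fewer than 5) | No estimate |
|---|---|---|---|---|
| 1% | 0.4 | 67% | >99.9% | 71% |
| 2.5% | 1.0 | 36% | 99.7% | 43% |
| 5% | 2.0 | 13% | 95% | 18% |
| 10% | 4.0 | 1.5% | 63% | 3% |
| 20% | 8.0 | <0.1% | 7.6% | about 0.1% |

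**5. Sensitivity, for rates of 1%, 2.5%, 5% and 10%.**
- A skewed baseline (26 plus a gamma variable, SD about 3.5; 2,000 runs) gives no estimate in 69%, 41%, 16% and 2%.
- The same with 32 subjects (an assumed 20% loss, 40 x 0.8) gives 76%, 48%, 25% and 6%.
- Remission is an absolute cut-off, easier to reach from a lower baseline. With an assumed log-odds slope of -0.7 per baseline SD in the Normal(31, 4) setting, the figures rise to about 75%, 48%, 22-23% and 5%.

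**6. Precision when the model fits.** Under the skewed baseline with N = 40, the median ratio of upper to lower 95% limit for the odds ratio per baseline SD is about 29 at a 5% rate, 11 at 10%, 5.5 at 20% and 4 at 50%.

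**7. The alternative.** Exact (Clopper-Pearson) 95% limits exist at any count: 0/40 gives 0-8.8%, 1/40 gives 0.1-13.2%, and 2/40 gives 0.6-16.9%.

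**The case against.** A reader might infer that 40 subjects are bound to yield too few events, so that all the early models fail. The documents do not support that. They give no early event rate, and at 10% the estimate exists in about 97% of simulated trials. Nor does the 16-17 point fall carry over to the other outcomes. Response needs less, and the CGI cut-offs cannot be read in the available text, so no count is argued for them.

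Four further points can be made against acting.

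- **Treatment might be meant to vary.** The safety section speaks of treatment groups, the BNA analysis mentions controls, and dose is flexible. But the subject population defines no second cohort, and dose is adjusted for tolerability after baseline. Nothing defines either as the treatment term.
- **Separate fits are an inference.** The text does not say that each visit gets its own model. It is the natural reading, and the treatment term is not estimable on any reading. A single unpenalised repeated-measures model with visit as a category would not help either, because a visit with no events again has no finite estimate.
- **The single-arm defect is the larger one.** This stands, and the point leads with it. Deleting the treatment term alone, however, leaves the sparse-event problem in place.
- **Little depends on these models.** This also stands. They are secondary analyses in a pilot whose primary objective concerns BNA change. No decision rule uses the Week 1-2 results, and a failed fit usually shows in the output.

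**Conclusion.** The point holds in two parts of different strength.

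- **Unconditional.** In a single arm the stated model gives no treatment odds ratio at any of Weeks 1-8, and adjusting for baseline is undefined for CGI-I. This rests on no assumption about rates.
- **Conditional.** If the event rate at a visit is about 5% or less, the baseline-only model often has no estimate (about 18% of trials at 5%, 71% at 1%), and fewer than 5 events are expected in at least 95% of trials. MADRS remission at Weeks 1-2 is the likeliest case. At 10% the model nearly always fits, with a 63% chance of fewer than 5 events and wide limits. These figures rest on assumed rates, an assumed baseline distribution, and no dropout unless stated.

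The documents do not show that early models will fail for every outcome, or that any main conclusion of the study would change. The priority is modest.

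**What to change.** In Secondary Efficacy Analyses, replace the logistic sentence along these lines:

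*At each of Weeks 1-8, each binary outcome will be reported as the number and proportion of subjects with an exact (Clopper-Pearson) 95% confidence interval. A logistic model with baseline score as the only covariate may be fitted at Week 8 as a supportive analysis. Firth's penalised likelihood will be used if events or non-events are few, with the threshold fixed in advance. For CGI-I the baseline score used will be named.*

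This drops the treatment term. An unpenalised repeated-measures logistic model should not be added as a substitute. The three printed MADRS remission cut-offs, and the two forms of the response rule (above 50% here, at least 50% under Outcome Definitions), should be reconciled at the same time, since the weekly counts depend on them.

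The cost is wording only, with no new data or visits. The small downside is that no baseline-adjusted odds ratio is reported before Week 8, including at middle visits where one might have been estimable.
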